#### 13.1.5.1 Exploratory Endpoints

Overall subject improvement as assessed by the clinician's rating on LSAS, CGI-S, CGI-I, and the subject's rating of the PGI-C from Screening (Visit 1) through Follow-up (Visit 15) will be summarized, including changes from baseline where appropriate. The change in LSAS, CGI-I, and PGI-C scores from Baseline to Visit 14 may also be explored using generalized linear model for repeated measures.

In addition, overall change in the pattern in the frequency of PH94B use (frequent users; 3 or 4 times a day and less frequent users;  $\leq$  2 times a day), change in medication use as documented by the clinician and the subject between Screening (Visit 1) and Follow-up (Visit 15) will be summarized.

Full details on this exploratory analysis will be provided in the SAP.

The exploratory endpoints are as follows:

- Change in total LSAS scores over time with use of PH94B
- Change in proportion of subjects with CGI-S scores  $>4$  over time with use of PH94B
- Change in proportion of subjects with CGI-I scores of 1 (Very much improved) or 2 (Much improved) over time with use of PH94B
- Change in proportion of subjects with PGI-C scores of 1 (Very much improved) or 2 (Much improved) over time with use of PH94B
- [REDACTED]
- [REDACTED]
- [REDACTED]

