4.2. Interim Analysis and Data Monitoring

No interim analyses are planned.

5. Analysis Populations

The following analysis populations are planned for this study:

- **Safety Population:** All subjects who are dispensed IP during Visit 2 (Baseline) will be included in the Safety population. All subjects will receive PH94B in an open label fashion. Adverse events (AEs) will be grouped by associated length of exposure and level of PH94B use.

Inclusion of subjects in the Safety Population will be determined prior to database lock.

6. General Issues for Statistical Analysis

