6.1.7. Derived Variables

6.1.7.1. General

- **Age** = Integer difference in years between the subject's date of informed consent and date of birth.
- **Change from Baseline to Visit X in Parameter Y** = Value at Visit X minus the value at Baseline (as defined in Table 2).
- **Percent Change from Baseline to Visit X in Parameter Y** = Change from Baseline to Visit X in Parameter Y divided by the value at Baseline (as defined in Table 2) multiplied by 100.
- **Shift from Baseline to Visit X in Parameter Y Categories** = Cross-tabulation of below the lower limit of the normal range, within the limits of the normal range, and above the upper limit of the normal range at Baseline (as defined in Table 2) versus at Visit X.
- **Height (cm) and Weight (kg)** = Height (cm) will be calculated as height (in) times 2.54. Weight (kg) will be calculated as weight (lb) times 0.4536.
- **Temperature (C°)** = Temperature (F°) -32 times 5 divided by 9.
- **Treatment duration** = Days in study (date of last Visit minus date of Visit 2 (Baseline)).
- **Days of exposure** = Date of Visit 14 (End of Treatment) minus date of Visit 2. [In the case Visit 14 is missing then the date of study completion will be used.]
- **PH94B use** = average weight of all 6 vials when dispensed – weight of all 6 vials when returned at subsequent visit, at each visit.

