7.5. Exploratory Efficacy Analysis

All exploratory endpoints will be summarized for descriptive purposes only.

The following variables will be summarized for all subjects completing each visit. All derived variables will be computed as described in Section 0.

Categorical data will report frequency of responses and proportion of responders by study visit:

1. Proportion of CGI-I responders will be assessed from Visit 3 to Visit 14 by study visit.
2. Change in proportion of PGI-C responders will be assessed from Visit 3 to Visit 14 by study visit.
3. Proportion of CGI-S scores > 4 by from Visit 2 to Visit 14 by study visit.

Continuous data will report descriptive statistics of observed values and change from baseline by study visit:

4. Change in LSAS total scores by visit.
5. [REDACTED]

8. Safety and Tolerability Analysis

Safety in this study will be evaluated based on data collected on AEs, clinical laboratory assessments, vital signs, 12-lead ECGs, PWC-20 (at Visit 14/15 End of Study/Follow-up), and physical examinations including examination of the nasal passages. As a precautionary measure, subjects will also be assessed using the C-SSRS and HAM-D at each study Visit.

All safety analysis reporting will be based on the Safety Population (as defined in Section **Error! Reference source not found.**). No formal statistical testing will be conducted for the safety analyses. Descriptive statistics will be used to evaluate safety data. Summaries will present data by overall subjects. Listings will list safety data by subject.

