8.1. Adverse Events

Treatment emergent AEs (TEAEs) are defined as:

- AEs with onset at the time of or following the start of treatment with IP through final Visit or follow-up phone call.
- AEs starting prior to the start of treatment with IP but increasing in severity or relationship at the time of, or following, the start of treatment with IP through Visit 14 (End of Treatment/Follow-Up).
- AEs that occur between Visit 14 and Visit 15.

Any medical condition that is present at the time that the subject is screened will be considered as baseline and not reported as an AE. However, if the study subject's condition deteriorates at any time during the study, it will be recorded as an AE.

The Investigator will record all reportable events with start dates occurring any time after informed consent is obtained until 7 days after the last day of study participation. Events will be followed for outcome information until resolution or stabilization. Missing and partially missing start dates will be imputed for the purpose of analysis as described in Section **Error! Reference source not found.**

All AEs, TEAEs, and serious AEs (SAEs) will be coded using the MedDRA dictionary, as discussed in Section **Error! Reference source not found.**

All AE data will be categorized as Severe > Moderate > Mild. Relationship of all AEs to IP will be categorized as related or not related. In the summaries showing severity and relationship to study drug, the event with the maximum severity or strongest relationship to study drug will be reported. If a particular event is missing the severity and/or relationship, then the strongest possible severity or relationship will be assumed for analysis (severity = severe, relationship = related).

An overall summary of TEAEs will be provided; this will present number and percent of subjects who reported at least 1 of the following: TEAE (including any TEAE, TEAEs by maximum severity, and related TEAEs), TEAE leading to discontinuation of the study drug, TEAE leading to discontinuation from the study, serious TEAEs, and SAEs leading to death. TEAEs will be summarized by two time periods (TEAEs which occur prior to Visit 14 and those that occur during or after Visit 14).

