In addition to the overall summary, summaries of the number and percentage of subjects with TEAEs will be displayed by overall by SOC and preferred term by time period. Summaries of TEAEs by severity (Severe > Moderate > Mild) and relationship to IP (Related > Not Related)

will also be provided. Serious TEAEs and TEAEs resulting in discontinuation of IP will be summarized separately in a similar manner.

Subject listings of AEs, SAEs, and AEs causing discontinuation of IP will be produced. Adverse events that are treatment emergent will be flagged.

The AE summary tables will include counts of subjects. Therefore, if a subject experiences more than 1 episode of a particular AE, the subject will be counted only once for that event. If a subject has more than 1 AE that is coded to the same preferred term, the subject will be counted only once for that preferred term. Similarly, if a subject has more than 1 AE within a SOC, the subject will be counted only once in that SOC. This will be handled separately for each time period (post-Visit 2 through Visit 15 [End of Treatment/Follow-up]).

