8.9. Coronavirus 2019 (COVID-19) Impact

The SARS-CoV-2 virus and variants may still be a threat and safety precautions may still be in place during study enrollment. To assess the impact of the COVID-19 pandemic on study

AD-ST-33.06 Effective date: 12-Nov-2020

procedures, study staff will complete the COVID-19 Impact questionnaire. Should a study Visit be affected by COVID-19, study staff will record how the Visit was affected (missed, abbreviated, delayed, performed remotely, or otherwise deviating from the planned format in the protocol) and which procedures were impacted. All COVID-19 protocol deviations will be provided in a separate listing. This listing will include the subjects, affected Visits, and affected assessments.

10. Changes from Planned Analysis

Endpoints removed: analysis not performed – data not collected.

Study staff will complete the Coronavirus 2019 (COVID-19) Impact questionnaire to assess the impact of the COVID-19 pandemic on study procedures. The COVID-19 Impact questionnaire is described in Section [8.9](#). All COVID-19 protocol deviations will be provided in a separate listing.

Exploratory objectives (changes in pattern of PH94B use daily frequency and dosing interval) requiring the use of eDiary data were removed due to unreliability of eDiary data.

The original planned interim safety analysis was removed from the study.

A qualitative review of categorical data was done instead of an assessment of a change in proportion over time due to limited availability of data.

11. References

ASA. (2018) Ethical Guidelines for Statistical Practice. Prepared by the Committee on Professional Ethics, April 2018. <http://www.amstat.org/about/ethicalguidelines.cfm>

Carpenter JR and Kenward MG. *Multiple Imputation and its Application (Statistics in Practice)*. Chichester, West Sussex, UK: John Wiley & Sons; 2013.

Graham JW, and Olchowski AE, Gilreath TD. (2007) “How Many Imputations are Really Needed? Some Practical Clarifications of Multiple Imputation Theory.” *Prev Sci.* 2007;8(3): 206-213.

ICH (1998). ICH Harmonised Tripartite Guideline. Statistical Principles for Clinical Trials E9; 1998. https://database.ich.org/sites/default/files/E9_Guideline.pdf

Little R and Rubin D. (1987). Statistical Analysis with Missing Data, New York: Wiley.

RSS. (2014) The Royal Statistical Society: Code of Conduct, 2014. <https://rss.org.uk/about/policy-and-guidelines/code-of-conduct/>.

12. Tables, Listings, and Figures

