14.3.1 Displays of Adverse Events		
Table 14.3.1.1	Safety	Overall Summary of Treatment Emergent Adverse Events
Table 14.3.1.2.1	Safety	Treatment Emergent Adverse Events by System Organ Class and Preferred Term
Table 14.3.1.2.2	Safety	Treatment Emergent Adverse Events by Preferred Term
Table 14.3.1.3	Safety	Treatment Emergent Adverse Events by System Organ Class, Preferred Term, and Maximum Severity

Table Number	Population	Table Title / Summary
Table 14.3.1.4	Safety	Treatment Emergent Adverse Events by System Organ Class, Preferred Term, and Maximum Relationship to Investigational Product

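### SAP 5 promises adverse events by level of drug use, but no planned AE summary delivers this and SAP 10 does not withdraw it

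*SAP*

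**What the plan says.** - **The commitment.** SAP 5 (Analysis Populations), under the Safety Population: "Adverse events (AEs) will be grouped by associated length of exposure and level of PH94B use".
- **The safety summaries.** SAP 8: "Summaries will present data by overall subjects". SAP 8.1: "TEAEs will be summarized by two time periods", meaning before Visit 14 and from Visit 14 on. The counts are "displayed by overall by SOC and preferred term by time period", with further summaries by severity and relationship.
- **The table list.** The AE titles in SAP 12.3 follow the same lines, for example "Treatment Emergent Adverse Events by System Organ Class, Preferred Term, and Maximum Severity". None names a level of use.
- **The measure of use.** SAP 6.1.7 defines PH94B use at each visit as "average weight of all 6 vials when dispensed" minus the weight of all six on return. SAP 7.4 summarises the average weight difference overall. There are no cut-points and no link to AEs.
- **The protocol's categories.** Protocol 13.1.5.1 distinguishes "frequent users; 3 or 4 times a day and less frequent users" (at most twice a day), for an exploratory summary of the pattern of use. The SAP does not carry them over.
- **What was withdrawn.** SAP 10 says that exploratory objectives on the pattern of use "requiring the use of eDiary data were removed due to unreliability of eDiary data". It does not mention the AE grouping.

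**The concern.** The SAP makes a commitment on the primary safety outcome that nothing later in it carries out. Subjects decide for themselves when to dose, and the protocol says that daily use is not required, so the Safety Population mixes frequent and occasional users. The study has one arm and no comparator, and no other planned output relates AEs to the amount of drug used. The two time periods in SAP 8.1 separate treatment from its end and follow-up, and say nothing about amount.

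If AEs become more common with heavier use, the planned tables would not show it. Safety is also framed as up to four doses a day for up to 12 months in up to 600 subjects. A reader could therefore take a low pooled rate, or the absence of an event, as evidence about frequent dosing that the table does not contain.

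**Working it through.** **1. Promise against delivery.** Neither document states a figure to reproduce, so the first check is textual. For AEs by level of use, a plan needs a measure, levels, a table and a denominator.

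- Measure: present (vial weight, SAP 6.1.7), but see step 2.
- Levels: none in the SAP.
- Table: none among the AE titles in SAP 12.3.
- Denominator: none by use.
- Withdrawal in SAP 10: none. That section removes objectives that needed eDiary data, and vial weights are not eDiary data.

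**2. Can vial weights carry the grouping?** Protocol 9.4 has each vial weighed before dispensing and on return, with weights entered in the eCRF. Protocol 9.1 and 9.2 give 100 µL a spray and two sprays a dose, so one dose is 2 × 0.1 = 0.2 mL. At *d* doses a day, use is 0.2 × 7 × *d* = 1.4*d* mL a week, or 6*d* mL in 30 days: 6, 12, 18 and 24 mL for *d* = 1, 2, 3 and 4. Broad bands are separable in principle. Two things need correction first.

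- *Formula.* As written it subtracts a total from an average. Take six vials of 8 mL, one dose a day for 30 days, contents only, 1 g per mL (assumed), no priming. The total dispensed is 48 and the total returned is 42. Like for like gives 48 − 42 = 6. The literal formula gives 8 − 42 = −34.
- *Priming.* Protocol 9.9.1 has vials weighed before priming and a fresh vial started each week, so primed spray counts as use. The current text gives no number of priming sprays. Assuming 1 to 5 per vial and 4 to 6 vials a month, priming is 4 to 30 sprays, or 2 to 15 dose-equivalents, or 0.07 to 0.5 doses a day over 30 days. At 10 sprays and 6 vials it would be 60 / 2 / 30 = 1.0 dose a day. This is a systematic upward bias.

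**3. Illustration of size.** The share of frequent users is not in the documents. The shares and rates below are assumptions.

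One-sided 95% upper bound for an event not seen in *n* subjects, 1 − 0.05^(1/*n*):

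- *n* = 600 (everyone): 0.50%
- *n* = 150 (25% frequent users): 1.98%
- *n* = 60 (10%): 4.87%
- *n* = 30 (5%): 9.50%

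Dilution, if an AE occurs in 15% of frequent and 5% of occasional users: with 10% frequent users the pooled rate is 0.10 × 15 + 0.90 × 5 = 6.0%. With 20%, 30% and 50% it is 7.0%, 8.0% and 10.0%.

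**The case against.** **The regimen is as needed.** The protocol's rationale and treatment regimen describe use as needed, up to four times a day, and the primary objective concerns repeated dosing over up to 12 months. Occasional users belong to that regimen. A reader might infer that the pooled AE rate fails the primary objective or describes only rare use. The documents do not support this: the pooled rate answers the objective as written, and nothing shows how often subjects dose. This part of the objection stands.

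**The protocol does not ask for AEs by use.** Protocol 13.1.4 plans AEs by exposure period, organ, relatedness, severity and AE frequency. The optional subgroups named in Protocol 13.1.1 do not include use. The SAP 5 clause may be a leftover, and deleting it would also end the contradiction. That is true, and is the fallback below. Deletion alone would still leave the pooled rate open to misreading.

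**The protocol's use categories have no gap as stated.** A reader might infer that use between two and three times a day is unclassified. Whole daily counts from zero to four are all covered. A gap appears only if the categories are applied to a subject's average, which Protocol 13.1.5.1 does not say.

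**The bounds are not planned outputs.** SAP 8.1 plans no bound for unobserved events and 600 is a ceiling. Splitting the table would not tighten the bound for a small group of frequent users; it would only make the small number visible. This stands.

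**Table shells.** SAP 13.2 lists shells that are not in the available text, so the absence of a use column is judged from the titles and the text of SAP 8.1.

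**Conclusion.** The inconsistency is real and concerns the primary safety outcome. SAP 5 commits to AEs by level of use, while SAP 8, SAP 8.1 and the table titles pool all subjects in that respect. SAP 10 neither withdraws nor replaces the commitment. The SAP should be changed.

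The consequence is limited. The pooled rate describes the as-needed regimen as used. It cannot show whether AEs rise with use, and it should not be cited as safety at frequent dosing. The contrast between 0.50% and 2.0% to 9.5% shows how much less may be known about frequent users. It rests on assumed shares of 25%, 10% and 5% of a full 600, with each subject in one fixed class. The conclusion about the text needs none of these assumptions.

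**What to change.** 1. **SAP 6.1.7.** Define use per dispensing interval as total dispensed weight minus total returned weight over all vials in the kit, less a fixed priming allowance per opened vial. Divide by days in the interval and convert to mean doses a day with a stated weight-to-volume factor. Treat intervals with lost or unreturned vials as unknown use, not zero.
2. **SAP 8.1.** Add one descriptive table of TEAEs by broad, contiguous use bands fixed before database lock. Assign each event by use in the interval of onset or the one before, and settle which in advance. The earlier interval is free of cutting back after the event, but does not exist for events in the first month. Whole-study average use should not be the basis. Give subjects and subject-months per band as denominators.
3. **Limits to state with the table.** eDiary data are not used. Use is self-selected, so differences between bands are not causal. A monthly mean weight cannot isolate days with three or four doses.
4. **Fallback.** If vial weights prove unusable, delete the SAP 5 clause, record the deletion in SAP 10, and state that pooled rates do not characterise frequent use.

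The cost is SAP text, programming of a corrected exposure variable, and one table, all from weights already recorded in the eCRF. The downside is a coarse measure of exposure and probably few subjects in the top band.

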6.1. Statistical Definitions and Algorithms

6.1.1. Baseline

The last observation recorded before the first dose of PH94B will be used as the baseline observation for all calculations of change from baseline.

Table 1: Baseline Definitions

Parameter	Baseline
Safety Variables (clinical laboratory assessments, vital signs, ECGs, physical examinations)	The last non-missing assessment before the first dose of study drug given at Visit 2 (Baseline).
C-SSRS Scores	Scores on the Baseline version of the C-SSRS given at Visit 1 (Screening).
LSAS total score, HAM-D total score, [REDACTED]	Total score at Visit 2 (Baseline).

Abbreviations: CGI-I = Clinical Global Impression of Improvement; ECG = electrocardiogram; C-SSRS = Columbia-Suicide Severity Rating Scale; [REDACTED] HAM-D = Hamilton Depression Scale; LSAS = Liebowitz Social Anxiety Scale

6.1.2. Adjustments for Covariates

No adjustments will be made for covariates.

6.1.3. Multiple Comparisons

No adjustments will be made for multiple comparisons.

6.1.4. Handling of Dropouts or Missing Data

Only observed data will be included in the final report.

6.1.5. Analysis Visit Windows

Analysis Visits will be assigned based on the nominal Visit recorded in the study database.

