**Urinalysis**  
**Macroscopic Panel:** bilirubin, blood, clarity, color, glucose, ketones, leucocyte esterase, nitrite, pH, protein, specific gravity, urobilinogen

**Urine Drug Screen:** If on-site urine drug screen is positive, urine sample will be submitted to central laboratory for confirmatory urine drug screen to be performed:  
opiates, cocaine, amphetamines, barbiturates, benzodiazepines, cannabinoids, methadone, phencyclidine, propoxyphene, methamphetamine, buprenorphine, ecstasy, and oxycodone

**Other:** thyroid stimulating hormone  
free thyroxine (T4) will automatically be performed if thyroid stimulating hormone level is above the upper or below the lower normal limits

The central laboratory should be used for any unscheduled and follow-up labs, if needed. Additional urine and blood samples may be collected for further evaluation of safety as warranted by the Investigator's judgment.

Results and reports from the central laboratory should be filed with the source documents for each subject. The central laboratory will provide laboratory results to the study site as soon as they are available; results will also be provided to the sponsor or designated data manager within agreed upon timelines.

Any laboratory value outside the normal range will be flagged for the attention of the Investigator, who must indicate whether or not the value is of clinical significance. If the result of any laboratory test performed during Screening is clinically significant, the subject should not be advanced to Visit 2 (Baseline) before discussing with the Medical Monitor. However, any abnormal result may be repeated to confirm the finding before excluding the subject from potential inclusion in the study. In addition, subjects should be excluded if they have any other abnormal laboratory test at Screening that, in the Investigator's judgment, is medically significant in that it would impact the safety of the subject, the conduct of the study, or the interpretation of the study results.

Follow-up/unscheduled laboratory tests may be performed on clinically significant abnormalities as indicated by the Investigator. Unscheduled laboratory tests may be repeated at any time at the discretion of the Investigator for appropriate medical care.

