8.2. Clinical Laboratory Evaluations

Descriptive summaries of observed values and change values will be presented for continuous hematology, chemistry, and urinalysis results for overall subjects at each study Visit. Ninety-five percent CIs for the change and percent change will be included. Categorical urinalysis results will be summarized using frequencies by overall subjects and by study Visit.

The number of subjects with clinical laboratory values categorized as below, within, or above normal ranges will be tabulated showing change from baseline (shift tables) for each clinical laboratory analyte by overall subjects and by study Visit.

Laboratory values that are outside the normal range will also be flagged in the data listings and presented with the corresponding normal ranges. Any out-of-range values that are identified by the investigator as being clinically significant will also be shown in a data listing.

For women only, pregnancy status will be determined by evaluation of urine pregnancy test.

Data on pregnancy status will be listed by subjects. Subjects who are pregnant are excluded from the study. Subjects who become pregnant during the study will be discontinued.

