8.3. Vital Signs

Descriptive summaries of observed values and changes from baseline will be calculated for systolic blood pressure (mmHg), diastolic blood pressure (mmHg), heart rate (beats/min), respiratory rate (breaths/min), and temperature (°C) by overall subjects and by study Visit.

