8.8. Hamilton Depression Scale (HAM-D)

Total scores and change from baseline will be summarized for the Safety population.

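### Laboratory shifts are tabulated only visit by visit with no rule for unscheduled results, so the described tables do not count subjects ever out of range; two protocol safety summaries are also missing from the SAP

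*SAP*

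**What the plan says.** SAP 6.1.5 sets the visit rule in one sentence: "Analysis Visits will be assigned based on the nominal Visit recorded in the study database". SAP 6.1.7.1 defines a shift as a cross-tabulation of range categories "at Baseline (as defined in Table 2) versus at Visit X". SAP 8.2 then states that laboratory categories "will be tabulated showing change from baseline (shift tables) for each clinical laboratory analyte by overall subjects and by study Visit". The three shift tables are 14.3.5.1.2 (hematology), 14.3.5.2.2 (chemistry) and 14.3.5.3.2 (urinalysis).

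Protocol 10.3.1.1.1 foresees laboratory samples outside the schedule: "Follow-up/unscheduled laboratory tests may be performed on clinically significant abnormalities as indicated by the Investigator". It also lets the investigator repeat tests at any time. The SAP does not say how such results enter a table.

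For vital signs, protocol 13.1.4.3 plans shift tables by visit. SAP 8.3 plans only observed values and changes, ending "and temperature (°C) by overall subjects and by study Visit", with no range categories. For ECG, protocol 13.1.4.4 plans the number and percentage of subjects with a change above 30 ms or above 60 ms, not tied to a visit. SAP 8.4 and Tables 14.3.6.2.1 to 14.3.6.2.3 do not mention that count. SAP section 10, which lists departures from the planned analysis, names neither item.

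**The concern.** This is a single-arm trial of up to 12 months whose primary objective is safety. A natural question for each laboratory analyte is how many subjects went out of range at any point on treatment. By-visit counts do not answer it, because they do not show whether the same subjects or different ones are out of range from month to month.

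The SAP already uses subject-level, any-time counting elsewhere. Section 8.6 reports an increase in the maximum C-SSRS score during treatment, and section 8.1 counts each subject once per preferred term within a time period. Laboratory data have no equivalent, and the one any-time ECG count in the protocol did not reach the SAP. At stake is whether the report can state an incidence of laboratory and QT changes without someone counting it by hand from listings.

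**Working it through.** **No figure to reproduce.** The sample size of up to 600 rests on ICH E1, with no rate, power or dropout assumption (protocol 13.2, SAP 3.2). The numbers below only illustrate what by-visit tables leave open.

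**Inputs**
- N = 600, the protocol's maximum.
- V = 12 post-baseline laboratory visits, Visits 3 to 14 (protocol Table 2-1).
- p, the proportion out of range at each visit for one analyte in one direction: assumed, from 0.5% to 5%.
- Full attendance at every visit: assumed.

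**Formulas**
- Subjects out of range per visit: k = N × p.
- Fewest ever out of range (the same subjects each time): k.
- Most ever out of range (different subjects each time): the smaller of N and k × V.
- If visits were independent: 1 − (1 − p)^V.

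**Worked case, p = 2%**
- k = 600 × 0.02 = 12.
- Minimum: 12 of 600 = 2%.
- Maximum: 12 × 12 = 144; 144 / 600 = 24%.
- Independent visits: 1 − 0.98^12 = 0.215, about 129 subjects. This lies inside the range and is not its upper end.

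| Per-visit rate | Per visit | Fewest ever | Most ever | Independent visits |
|---|---|---|---|---|
| 0.5% | 3 | 3 (0.5%) | 36 (6%) | 5.8% (35) |
| 1% | 6 | 6 (1%) | 72 (12%) | 11.4% (68) |
| 2% | 12 | 12 (2%) | 144 (24%) | 21.5% (129) |
| 5% | 30 | 30 (5%) | 360 (60%) | 46.0% (276) |

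Within each row, the per-visit count of out-of-range subjects is the same throughout the range.

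**Unscheduled laboratory results.** The SAP's silence leaves two readings. If a repeat is stored under an unscheduled label, the shift definition gives it no row. If it is stored under the scheduled visit, that visit has two values and no rule for choosing between them. The only replicate rule in the sections concerned is the mean of triplicate ECG reads in SAP 8.4.

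**Protocol against SAP**
- Vital-sign shifts: in protocol 13.1.4.3; not in SAP 8.3. Table 14.3.6.1 covers observed results and change only.
- QT change counts: in protocol 13.1.4.4; not in SAP 8.4 or in any ECG table title.
- SAP section 10 records the loss of the interim analysis and of the eDiary endpoints, but neither of these. Its general reason for removed endpoints, that data were not collected, does not fit, because the SAP still summarises both vital signs and QT.

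**The case against.** The strongest reply is that much of the information is reported elsewhere.

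- **Adverse events.** Protocol 10.3.1.1.3 requires clinically relevant laboratory changes to be reported as AEs. Protocol 11.1.1 adds abnormalities that a repeat test does not refute, that suggest disease or organ toxicity, or that need active management. These reach the TEAE tables, which give subject-level rates. This stands. What remains uncounted is mainly out-of-range values not recorded as AEs.
- **Listings and extremes.** SAP 6.1.8 lists all data, Tables 14.3.4.1 to 14.3.4.3 list abnormal laboratory values by subject, and SAP 4.1 includes the minimum and maximum in each continuous summary. So it would be wrong to infer that peak values are lost: each visit's extremes are shown. Listings still give no rate.
- **Unscheduled results.** A reader might infer that repeats are excluded and that the most extreme values therefore vanish. The SAP does not say so. An unscheduled pre-dose laboratory value can serve as baseline under SAP 6.1.1. The protocol sentence describes follow-up of abnormalities already found, so the first value may well sit in a scheduled visit's row. It also concerns laboratory tests only and cannot be carried over to vital signs, ECG or HAM-D17.
- **By-visit labelling.** The hematology and urinalysis shift titles lack the by-visit label that the chemistry title has, and the QT text in SAP 8.4 refers to a post-Visit 2 period. The definition in 6.1.7.1 and the text of 8.2 still make laboratory shifts by visit. The QT text plans only summary statistics, and Table 14.3.6.2.3 is by visit.
- **HAM-D17.** SAP 8.8 says "Total scores and change from baseline will be summarized for the Safety population", and a reader might call the lack of a category a defect. The endpoint is change in score, which that serves. A score below 18 is an entry limit, not a safety threshold; protocol 10.3.2.3 separately describes 20 or more as at least moderate depression. A category is optional.
- **Table shells.** The SAP contents announce shells in section 13.2. They are not part of the text on which this point rests, and they could hold extra rows. The point concerns the tables as described in the SAP text and table list.

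**Conclusion.** The point holds for laboratory data. As described, no summary table gives the number of subjects with an out-of-range value at any time after baseline, and no rule covers unscheduled results. The possible spread is wide: at an assumed 2% per visit, the same by-visit counts fit 12 to 144 of 600 subjects. That range rests on assumed rates, a constant rate across visits and full attendance, so it shows how little the by-visit tables settle and predicts nothing about this trial.

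For ECG and vital signs the firm finding is a discrepancy between documents: the protocol's QT change counts and vital-sign shifts are absent from the SAP without a recorded reason. The documents do not support the stronger claims that unscheduled values are dropped, that peaks are hidden, or that abnormalities have no rate at all. This is a cheap improvement, not a flaw that undermines the trial.

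**What to change.** 1. In SAP 6.1.5 and 8.2, add a worst post-baseline shift to Tables 14.3.5.1.2, 14.3.5.2.2 and 14.3.5.3.2. Take the highest and lowest values separately, using scheduled, unscheduled and early termination results (for qualitative urinalysis, the most abnormal category). Keep the by-visit shifts.
2. State which value fills a by-visit row when a visit has repeats.
3. Restore the protocol's QT change counts as n (%) of subjects at any post-baseline assessment. Say whether the change is in QT or QTcF, since protocol 13.1.4.4 does not.
4. Restore the vital-sign shifts. If either protocol item is to stay out, record that and the reason in SAP section 10.
5. Optionally, add an any-time HAM-D17 category, using a cut-off that the protocol itself gives.

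The cost is a paragraph in the SAP and a few table rows; no new data are needed. The downside is that worst-value tables overstate persistent abnormality, since one transient value counts as much as a lasting one. That is why both views should be shown.
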